The results of our recent LMA trial indicate that surfactant delivery via LMA produces immediate improvements in oxygenation comparable to delivery via ETT, and decreased need for subsequent ventilatory support. However, because our previous INSURE approach for ETT delivery of surfactant included morphine, a slow-onset, long acting analgesic which likely contributed to the need for invasive ventilation, it remains unclear whether LMA delivery of surfactant is as effective as our new INSURE technique, which is designed to avoid respiratory depression.

Since our last trial began, the results of a small randomized trial were published, where the 11 babies who received surfactant via LMA showed improvements in oxygenation comparable to those in our study, whereas no change occurred in the surfactant-untreated (CPAP-only) group (Attridge, Stewart, Stukenborg, & Kattwinkel, 2013). In a piglet model of RDS, surfactant administered via LMA had physiologic effects similar to those of ETT administration (Roberts et al., 2010). The only ongoing clinical trial on delivery of surfactant via LMA to human neonates with RDS (Roberts et al., NCT01116921 at www.clinicaltrials.gov) is examining the effectiveness of this procedure (versus no surfactant treatment) in decreasing the need for later mechanical ventilation.

From the foregoing, it is apparent that clinical trials are still needed to address the relative efficacy of surfactant delivered via LMA versus optimized INSURE approaches. In this proposal, we extend our investigations of surfactant delivery by LMA to the current clinical context in which premedication for INSURE comprises atropine and remifentanil.

Hypothesis:

Surfactant therapy delivered via LMA is not inferior to surfactant therapy delivered via transient intubation (INSURE technique) with short-acting narcotic premedication for mild to moderate RDS in preterm neonates.

Aims:

1. To compare the rate of failure of surfactant therapy delivered via LMA to the rate of failure of surfactant therapy delivered via transient intubation (INSURE technique) in avoiding mechanical ventilation in neonates 27 to 36 weeks' gestation with mild to moderate RDS.

1a. To evaluate the success of remifentanil as premedication for transient intubation (INSURE technique) as compared to morphine used in our previous trial.

2. To further evaluate the safety of surfactant administration via LMA.

B. Study Design/C. Subject Population

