Although the study interventions are limited to the airway used for surfactant administration in the first 1 to 3 days of life, and clinical management or follow-up are not otherwise conditioned by the study, all subjects enrolled will continue in the study up to discharge from AMC, for the purposes of data collection. This will include:

- the FiO₂ and mode of respiratory support before enrollment and at 0, 1, 12, 24, and 48 hours, and 7 and 28 days after initial surfactant administration,
- any need for additional doses of surfactant,
- any need for intubation, and
- any need for mechanical ventilation.

D. Data Analysis

A copy of the data collection sheet that will be used for the study is included.

Primary Outcome Measures: The primary outcome will be success of the surfactant administration strategy in avoiding mechanical ventilation in the first 120 hours of life.

Secondary Outcome Measures:

- Number of surfactant doses
- Days on assisted ventilation
- Day on any noninvasive respiratory support (CPAP/NIPPV modes)
- Days until off respiratory support (supplemental oxygen and/or pressure support)
- Rate pneumothorax and/or pneumomediastinum
- Rate of BPD as defined by oxygen dependence at later of 28 days or 36 weeks' postmenstrual age
- Complications during insertion of LMA or ETT
- Mortality rate

Planned post-hoc analyses include timing of failure by treatment group, which should illuminate the mechanisms of failure by treatment strategy.

➤ Baseline comparability:

Baseline differences between ETT group and LMA group will be compared using t-tests for continuous variables (birth weight, gestational age, age and FiO₂ at enrollment) and chi-square test for categorical variables (race, sex, prenatal care, antenatal steroids, mode of delivery, multiple gestation)

➤ Primary outcome measure:

Our primary outcome for the study is the proportion of infants that will reach the early and/or late failure criteria. The incidence of the failure criteria will be compared using chi-square statistics.

➤ Sample size/Power analysis:

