(Marshall, 1984). ETT insertion causes pain and discomfort, coughing, laryngospasm, and vagal responses including apnea and bradycardia; it may cause trauma to the airway including the vocal cords, subglottic edema, and stridor; more than one attempt at insertion is usually necessary, and esophageal intubation is common, requiring re-intubation. As many as 21% of "successful" tracheal tubes end up in a mainstem bronchus (Hipolito et al., 2001), which can cause trauma, hypoventilation, desaturation, pneumothorax, cardiac arrest, and asymmetric delivery of surfactant.

The hemodynamic effects of laryngoscopy and intubation are expected in most subjects during the procedure; we will follow our current procedures for intubation; this includes continuous monitoring of heart rate and SpO₂ throughout the procedure, and a post-intubation chest X-ray to verify the ETT position, if the ETT is to remain in place.

The adverse physiologic consequences of laryngoscopy and intubation can be attenuated with the appropriate use of premedication (VanLooy, Schumacher, & Bhatt-Mehta, 2008; Sarkar, Schumacher, Baumgart, & Donn, 2006; Greenwood & Colby, 2009). Premedication with intravenous remifentanil and atropine will be used, as per current practice (standardized order set). Remifentanil is a synthetic opioid with a half-life of only 3-5 minutes. It could cause adverse effects such as hypotension and bradycardia (Penido, 2010; Welzing, 2009). There have been reports in the literature of remifentanil causing chest wall rigidity (Choong, 2010), however, this was at higher doses. Remifentanil has successfully been used for INSURE at lower doses without any adverse effects (Welzing, 2009). If there is any concern of chest wall rigidity in this trial, the infant will be given naloxone, and, if necessary, vecuronium.

Decreased exposure to endotracheal intubation-related procedures among study patients would be expected to decrease the risks and discomfort associated with this method.

Atropine is an anticholinergic drug, used commonly in conjunction with other medications to reduce episodes of bradycardia by decreasing vagal responses. Bradycardia can result from vagal stimulation during laryngoscopy, endotracheal intubation, or insertion of the LMA. Tachycardia, restlessness, impaired gastrointestinal motility and dry secretions could be potential secondary effects observed.

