LMA insertion may result in kinking or malposition of the device, which may result in obstruction at the base of the tongue. In this case the mask must be removed and the procedure restarted. The overall incidence of complications after removal of the LMA is about 10-13%, including coughing, laryngospasm, retching, breath holding, vomiting, stridor, desaturation and excessive salivation (Trevisanuto, Micaglio, Ferrarese, & Zanardo, 2004; Schmiesing & Bock-Utne, 1998). A survey of almost 12000 patients of all ages managed with LMA over a period of 2 years reported only 0.15% (18) critical incidents related to airway management, and none required intensive care management (Trevisanuto et al., 2004).

We will use Infasurf®, sterile intratracheal suspension of calf lung surfactant extract, FDA approved for prophylaxis and treatment of RDS (Infasurf package insert, ONY, Inc.; available at www.infasurf.com). The most common adverse reactions with Infasurf dosing procedures are cyanosis (65%), airway obstruction (39%), bradycardia (34%), reflux of the surfactant into the ETT (21%), requirement of manual ventilation (16%) and re-intubation (3%). These events were generally transient in the controlled trials with Infasurf. If any one of these events occurs the administration of the surfactant will be interrupted until the neonate's condition is stabilized. Other conditions observed in trials of prophylaxis using Infasurf were incidence of pneumothorax (10%); the overall incidence of pneumothorax in our recent rescue treatment trial was 17%, similar in both groups. If a pneumothorax is suspected, transillumination and/or chest X-ray will be done, and the pneumothorax is managed according to the clinicians' judgment.

Adverse events (AEs):

An AE is any untoward clinical occurrence including sign(s), symptom (s), and/or laboratory finding(s) concurrent with the use of a drug or device in humans. AEs include worsening of any baseline symptoms. An AE need not have a causal relationship with the use of the drug or device. AEs may be detected by the investigators, or other competent observers. The investigators will also evaluate significant changes in laboratory values and imaging results; if they determine that a laboratory or imaging abnormality is clinically significant, it will be documented, along with a determination of whether or not the abnormal finding is consistent with the current diagnoses.

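### The device-complication outcome stops at insertion, so the planned LMA-versus-ETT comparison omits instillation and removal events and cannot fully answer Aim 2

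*Combined protocol and SAP*

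**What the plan says.** Aim 2 is stated as "To further evaluate the safety of surfactant administration via LMA". In section D, the one secondary outcome about the device procedure is "Complications during insertion of LMA or ETT". Secondary outcomes are the ones compared between groups, with chi-square tests for categorical data.

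Section E describes harms at several stages:

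- Removal, LMA: "The overall incidence of complications after removal of the LMA is about 10-13%, including coughing, laryngospasm", followed by retching, breath holding, vomiting, stridor, desaturation and excessive salivation.
- Insertion, LMA: "LMA insertion may result in kinking or malposition of the device".
- Insertion, ETT: pain, coughing, laryngospasm, apnea and bradycardia; also "it may cause trauma to the airway including the vocal cords, subglottic edema, and stridor".
- Instillation: airway obstruction, bradycardia and reflux are attributed to Infasurf dosing. The expected-AE table lists them under the surfactant administration procedure.
- Premedication, control arm: "There have been reports in the literature of remifentanil causing chest wall rigidity", at higher doses than planned here. Hypotension and bradycardia are also named.

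Under Reporting period, non-serious AEs in both arms are recorded from consent to 72 hours after the last use of the LMA or ETT, and serious AEs for longer.

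**The concern.** The comparison that the plan commits to in advance covers one phase of a procedure with several. The overall LMA complication rate that the protocol quotes belongs to another phase. Section E also places the same events at different stages for the two devices: coughing, laryngospasm and stridor are linked to insertion for the ETT and to the period after removal for the LMA. Read literally, laryngospasm at intubation counts towards the outcome and laryngospasm at LMA removal does not.

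Aim 2 is at stake. An insertion-only result describes part of the procedure's safety. Any fuller comparison would have to be assembled from AE forms after the data are seen.

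**Working it through.** **Group size.** The only sample-size figure in the plan is 65 per group. Inputs from section D: 70% success for the LMA, margin 20 points, one-sided alpha 0.05, power 80%. An equal INSURE rate is my assumption.

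n = (1.645 + 0.842)² × (0.7 × 0.3 + 0.7 × 0.3) / 0.20² = 6.18 × 0.42 / 0.04 ≈ 64.9, so 65 per group and 130 in total. This matches the plan. The point here uses only the 65.

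**What the insertion-only wording covers**

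| Phase | Events named in section E | In the outcome as worded? |
|---|---|---|
| Premedication | Chest wall rigidity, hypotension, bradycardia (remifentanil, control arm only) | No |
| Insertion | ETT: coughing, laryngospasm, airway trauma, misplacement. LMA: kinking, malposition, obstruction, bradycardia | Yes |
| Instillation | Airway obstruction 39%, bradycardia 34%, reflux | No |
| Removal | LMA: 10-13% overall. ETT: no rate given | No |

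**Expected removal events in the LMA arm**

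- 65 × 0.10 = 6.5 and 65 × 0.13 = 8.45 infants.
- Probability of at least one: 1 − 0.90^65 = 0.9989 and 1 − 0.87^65 = 0.9999.

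**Expected instillation events per arm, if the table's rates applied equally to both arms**

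- 65 × 0.39 = 25.35 infants with airway obstruction.
- 65 × 0.34 = 22.1 infants with bradycardia.

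**Does the omission favour one arm?** This needs an ETT post-removal rate, which the documents do not give. Over an assumed range, the omitted difference (LMA minus ETT, percentage points) is:

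| Assumed ETT rate | LMA 10% | LMA 13% |
|---|---|---|
| 0% | +10 | +13 |
| 5% | +5 | +8 |
| 10% | 0 | +3 |
| 13% | −3 | 0 |
| 20% | −10 | −7 |

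The sign changes within the range, so the documents do not settle the direction.

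**Does another planned analysis compare these events?** Pneumothorax or pneumomediastinum and mortality are compared. Early Failure, part of the analysed primary outcome, counts infants ventilated within 1 hour of surfactant. The interim review looks for a consistent trend in major adverse events. None of these counts a laryngospasm, desaturation or reflux episode that resolves without ventilation. The expected-AE table has an open line for other events but no removal or extubation item. Detailed reporting to the IRB is limited to AEs not explained by the underlying illness, and desaturation in a preterm infant with RDS can readily be put down to that illness.

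**The case against.** The strongest reply is that the gap is one of wording. AEs in both arms are recorded to 72 hours after last device use, investigators monitor for device-related events, and the expected-AE table names the instillation events. Deterioration severe enough to need ventilation within an hour is already in the primary outcome. The data collection sheet, which the protocol says is included, is not in the text available to me and may have a removal item. All of this stands as regards capture. It does not supply a planned final comparison, and a removal item on the form would not change the outcome as written.

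A reader might infer that the window covers the ETT's risk period, misses the LMA's, and so favours the LMA. The documents do not support that:

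- The wording applies to both devices.
- LMA insertion hazards fall inside the window, and LMA replacement is expected in 5 to 10% during the procedure.
- Subglottic edema and stridor from the ETT may show only after extubation, outside the window.
- Leaving out premedication effects omits remifentanil harms that arise only in the control arm, which would pull the other way.

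It is also fair to say that the 10-13% mixes minor events such as coughing and salivation with laryngospasm, and that no ETT figure stands against it. It sizes what is left out of one arm and does not size a between-arm bias.

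**Conclusion.** The gap is real and of moderate importance. The one device-complication outcome compared between arms excludes removal events expected in about 6.5 to 8.5 of 65 LMA infants, and also excludes instillation and premedication events in both arms. No other final comparison is planned for them, so the insertion-only result can answer Aim 2 only in part.

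The LMA count assumes that the quoted literature rate carries over to preterm infants with RDS, which the documents do not show. The instillation counts assume equal rates in the two arms. The direction and size of any bias between arms are unknown, and a claim that the plan is tilted towards the LMA should not be made from this text. The primary outcome and the sample size are unaffected.

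**What to change.** In section D, replace the insertion-only item with procedural complications from the start of premedication through insertion, instillation and device removal. End the window at one fixed time measured from the end of surfactant instillation in every infant, so that infants who stay intubated have the same window as those whose device is removed.

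The end time must be late enough to cover removal. The protocol allows extubation up to 15 minutes after surfactant is complete and gives no upper limit for LMA removal, so a 15-minute window would be too short. The 1 hour already used for Early Failure is one candidate. The definition should also say what starts the clock if instillation is not completed, and that each infant is counted once, for the first surfactant procedure.

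Use one event checklist in both arms, report events by phase, and compare arms with the chi-square test already planned for categorical secondary outcomes. An estimate with a confidence interval should go with it, because power is limited: for 10% versus 5% with 65 per arm it is about 19% at two-sided 0.05.

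The cost is a revised outcome definition and a phase column on the procedure form. Monitoring and AE recording already span the period, and neither treatment nor sample size changes. The downside is that reported complication rates rise in both arms and the form is slightly longer.

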- Multi-center, randomized controlled trial. The participating centers are Albany Medical Center, Bellevue Woman's Center at Ellis Hospital, and Golisano Children's Hospital. Each center will obtain approval from that center's own Institutional Review Board. It is anticipated that the study will take 2 years to complete.

[figure not shown]
Patient Enrollment:

- The investigators and/or study coordinator will evaluate all infants admitted to the NICU who are less than 48 hours of life from 27 through 36 completed weeks' gestation with mild-moderate RDS.
- If they meet the pre-defined inclusion criteria and informed consent is obtained, they will be randomized to either the INSURE group or LMA group for the initial surfactant administration. Patients will be block randomized in one of three gestational age groups: 27 0/7 - 28 6/7 weeks, 29 0/7 - 32 6/7 weeks, 33 0/7 - 36 6/7 weeks.
- Randomization process: An anticipated 130 patients will be enrolled in the study. Patients will be randomized into three groups using a blind randomization selection method. After computer-generated block randomization, the 130 numbered cards will be placed in sealed, numbered envelopes, and kept in a NICU nurse practitioner office. Each card will indicate LMA or INSURE group and include an identifier code number. After obtaining the signed consent form, the investigators or coordinator will open the next envelope in the appropriate gestational age block.
- Inclusion Criteria:
 - Gestational age (GA) 27 0/7 weeks to 36 6/7 weeks
 - Age < 48 hours
 - Mild-moderate RDS as defined by an FiO₂ requirement of 0.30 - 0.60 on either CPAP or nasal intermittent positive pressure ventilation (NIPPV) for at least two hours to maintain SpO₂ 90-95%
 - Written consent obtained
- Exclusion Criteria:
 - Prior tracheal intubation

- Prior surfactant therapy
- Evidence of pneumothorax, pneumomediastinum, or pneumopericardium
- $\text{FiO}_2 > 0.60$
- Craniofacial or other airway malformation
- Major congenital malformation (cardiac and thoracic defects)
- Apgar score of ≤ 3 at 5 minutes of life or evidence of encephalopathy
- Weight less than 800 grams

Study/Intervention:

The diagram below is a graphic depiction of the study protocol. Criteria for assisted ventilation and other respiratory support will be the same for both groups.

• **INSURE (control group): Atropine + remifentanil + intubation (ETT) + Infasurf**

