The sample size was estimated based on results from the recent study on this population, at the Albany Medical Center NICU. We will thus expect that 30% of the LMA group will meet failure criteria, i.e., the LMA success rate in avoiding later intubation and ventilation will be 70%. For a non-inferiority design, with a clinically relevant non-inferiority margin of 20%, a sample of 130 patients (65 per group) will be needed to conclude non-inferiority of the LMA method compared to INSURE (calculated using a one-sided $\alpha=0.05$, β error=0.20).

➤ Secondary outcome measures:

Groups will be analyzed for secondary outcome differences using chi-square statistics for categorical data, and t-test or non-parametric tests for continuous data, as appropriate for the distribution obtained. The FiO_2 response to surfactant treatment strategies will be compared from baseline to 1 and 8 hours using repeated measures ANOVA and post-hoc Dunnett's test. Time to wean off respiratory support will be compared between groups using Kaplan-Meier analysis, with censoring at discharge.

➤ Interim Analyses:

Reports for the IRB will be prepared after one year of initiation of the trial or enrollment of 50 patients, whichever comes first. Data on the primary outcome, mortality, and major adverse events on the first 50 patients, will be submitted to [name] for purposes of safety monitoring. A difference in primary outcome at the $p<0.01$ level, or a consistent trend towards differences in major adverse events will constitute criteria for recommending that the study be stopped.

E. Risks

- Risk category: Greater than minimal.

This study is considered as a greater than minimal risk study. The study design includes a decreased use of laryngoscopy for tracheal intubation, which is currently the standard method of surfactant delivery. Laryngoscopy is associated with apnea, minor abnormalities in cardiac rhythm, obstructed respiration, increase in systolic blood pressure, decreased heart rate and transcutaneous oxygen tension in preterm neonates during the laryngoscopy (Carbajal, 2007)

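### Enrollment FiO2, tied to the failure criteria and already recorded, is left out of the primary analysis along with the gestational-age strata: a cheap improvement, not a validity fault

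*Combined protocol and SAP*

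**What the plan says.** Under Patient Enrollment, the inclusion criteria read "Mild-moderate RDS as defined by an FiO₂ requirement of 0.30 - 0.60 on either CPAP" or nasal intermittent positive pressure ventilation. Randomization is in blocks within three gestational-age groups; FiO2 is not a stratification factor.

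Under Failures, the 0.60 level appears in both the early and the late criteria. It also appears among the indications for ventilation in each arm (Study/Intervention) and in the re-dosing criteria.

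In section D, Baseline comparability: "Baseline differences between ETT group and LMA group will be compared using t-tests for continuous variables". The list in brackets includes FiO2 at enrollment. No action is attached to the result. Under Primary outcome measure: "The incidence of the failure criteria will be compared using chi-square statistics". No covariate, stratum, risk difference or confidence bound is named. Baseline FiO2 enters one other analysis, the secondary repeated-measures ANOVA of FiO2 response.

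Under Sample size/Power analysis: "We will thus expect that 30% of the LMA group will meet failure criteria", and "a sample of 130 patients (65 per group) will be needed to conclude non-inferiority" with a 20% margin, one-sided alpha 0.05 and beta 0.20.

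**The concern.** Few baseline variables have so direct a link to an endpoint: entry FiO2 lies on the same scale as part of the failure definition and its upper limit meets the failure threshold. If infants entering with higher FiO2 fail more often, a chance difference in mean FiO2 between arms moves the observed failure difference, in either direction, against a fixed margin.

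The planned t-test does not help. Allocation is random, so the test has no useful null hypothesis. A non-significant result does not show that an imbalance is harmless, and the plan says nothing about what follows a significant one. The gestational-age strata, which the design took the trouble to balance, are also absent from the primary analysis. At stake are some precision and some protection against an unlucky allocation, both available from data already collected.

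**Working it through.** **1. The plan's own figure.** Inputs from Sample size/Power analysis: 30% failure with LMA, margin 0.20, one-sided alpha 0.05, power 0.80. No INSURE rate is stated for this trial; I take it as equal, which reproduces the stated size.

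n per arm = (1.645 + 0.842)² × (0.30×0.70 + 0.30×0.70) / 0.20² = 64.9, so 65 per arm and 130 in all. The stated size reproduces without any adjustment.

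**2. Room inside the margin.** SE of the risk difference = √(2 × 0.21/65) = 0.080. One-sided 95% half-width = 1.645 × 0.0804 = 0.132. LMA may therefore look at most 0.200 − 0.132 = 0.068 worse and still pass.

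**3. Size of a chance imbalance (assumed spread).** The documents give the range 0.30-0.60 but no SD. Assume FiO2 = 0.30 + 0.30 × Beta(1.3, 2.0), which is skewed toward 0.30 with SD 0.0707. SE of the arm difference = 0.0707 × √(2/65) = 0.0124. The edge of a two-sided 5% t-test is 1.96 × 0.0124 = 0.024. For SDs of 0.05 to 0.087 (the latter a uniform spread) the edge is 0.017 to 0.030.

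**4. Shift in the risk difference at that edge (assumed gradients, average failure 30%).** The first two rows use a logistic gradient. The last three use a linear one, where shift = slope × 0.0243.

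| Failure risk, FiO2 0.30 to 0.60 | Odds ratio across the range | Shift at edge |
|---|---|---|
| logistic | 2 | 1.2 points |
| logistic | 3 | 1.9 points |
| 15% to 53% | 6 | 0.38/0.30 × 0.0243 = 3.1 points |
| 10% to 61% | 14 | 0.51/0.30 × 0.0243 = 4.1 points |
| 5% to 69% | 42 | 0.64/0.30 × 0.0243 = 5.2 points |

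Only about 5% of trials have an imbalance this large in either direction. At the 10%-61% gradient the median absolute imbalance shifts the difference by 0.674 × 0.0124 × 1.7 = 0.014, or 1.4 points, against an SE of 8.

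**5. Power when the arms are truly equal, unadjusted then FiO2-adjusted.**
- No association: 80.5% to 79.5% (20,000 simulated trials, linear-model adjustment).
- Odds ratio 2 and 3: 80.0% to 80.2% and 80.0% to 80.5% by normal approximation, which ignores the cost of estimating the slope. Simulation over odds ratios 1 to 3 gives essentially no gain, or a loss under 1 point.
- Odds ratio 6, 14, 42: 80.6% to 81.0%, 80.2% to 81.6%, 79.8% to 83.4% (6,000 trials each). Repeat simulation put these gains at about 1 to 4 points. The Monte Carlo error of one power figure is √(0.8 × 0.2/6,000) = 0.5 points.

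**6. Error rates.** With uniform FiO2 and odds ratios of 1.5, 2 and 3 per SD (about 4, 11 and 45 across the range, since 0.30/0.0866 = 3.46 SDs), the unadjusted type I error over all randomizations is 4.3% to 4.5%. In the subset where LMA has the higher mean FiO2 with t between 1.2 and 1.96, unadjusted power is 73%, 68% and 61%, against 81%, 83% and 87% adjusted. With the reverse imbalance and a true 20-point deficit, false non-inferiority is 6.8%, 10.3% and 11.8% unadjusted, against 3.9%, 4.7% and 4.4% adjusted. Each one-sided subset is about 9% of trials (0.115 − 0.025).

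The gestational-age strata were not simulated; the documents give no failure rates by stratum.

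**The case against.** The strongest reply is that nothing is broken. Chance imbalance is already part of the sampling variance, the type I error holds, and the planned power was calculated for an unadjusted difference. That stands. A reader might infer that the omission biases the non-inferiority conclusion or leaves the trial underpowered; steps 1 and 6 show that it does neither.

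The prognostic strength of entry FiO2 is also unproven here. It is measured before surfactant, which the background says improves oxygenation at once. Infants also fail through apnea, retractions, re-dosing, or ventilation within 120 hours. The only evidence on mechanism in the documents attributes earlier INSURE failures to morphine. This stands too, and is why weak and null gradients belong in the range. A reader might take the 4-point shift, a fifth of the margin, as typical; it is a tail case under an assumed slope. The conditional error rates in step 6 likewise describe selected allocations, and the steepest gradient there is extreme.

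Finally, the plan defines no non-inferiority estimate at all, only a chi-square. That is a separate and larger gap and adds no weight to this one. None of this is a reason to leave out a variable that the endpoint's own wording points to.

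**Conclusion.** The primary analysis omits enrollment FiO2 and the gestational-age strata. Both are known for every infant at entry, and one is written into the endpoint. The unadjusted comparison remains valid on average over randomizations. The cost is unused precision and an estimate not corrected for the severity imbalance that happens to occur.

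The power at stake runs from about −1 to 0 points (odds ratio 1 to 3 across the entry range) to about +1 to +4 points (odds ratio 6 to 42). An imbalance at the t-test edge shifts the risk difference by about 1 to 4 points, or more at the steepest gradient, compared with 6.8 points of room. All of this rests on assumed FiO2 spreads and gradients and on equal failure rates of 30%. It is a cheap improvement, not a required correction.

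**What to change.** Before outcomes are examined, pre-specify the primary analysis as follows:

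- Fit a logistic model with arm, continuous enrollment FiO2 and gestational-age stratum, and convert it to a standardized risk difference.
- State the variance method, for example influence-function or bootstrap.
- Compare the one-sided 95% bound with the 20-point margin, whatever the baseline table shows. This also prevents adjustment from being chosen after an imbalance is seen.
- Report the unadjusted risk difference as supporting.
- Present baseline data descriptively, with no decision resting on baseline p-values.

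The cost is a change of SAP wording, slightly more analysis work, and a loss of about 1 power point or less if FiO2 turns out not to be prognostic. No new data are needed: FiO2 is recorded before enrollment and is needed to establish eligibility. The sample size stays at 130.

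### Siblings from multiple births can be enrolled, but no sibling allocation rule is stated and every planned between-group test treats infants as independent; the likely effect is small and slightly conservative

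*Combined protocol and SAP*

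**What the plan says.** - **Enrollment.** The exclusion criteria under Patient Enrollment do not mention multiple births. Section D (Baseline comparability) plans a "chi-square test for categorical variables (race, sex, prenatal care, antenatal steroids, mode of delivery, multiple gestation", so infants from multiple pregnancies are expected.
- **Randomization.** Allocation is blocked within three gestational-age groups, with no block size given. After consent, "the investigators or coordinator will open the next envelope in the appropriate gestational age block". Nothing says whether siblings are randomized separately, kept together, or limited to one per family.
- **Primary analysis.** The outcome is a proportion of infants: "The incidence of the failure criteria will be compared using chi-square statistics".
- **Secondary analyses.** Section D names chi-square, t-tests or non-parametric tests, repeated measures ANOVA and Kaplan-Meier. None is described as allowing for family membership.
- **Sample size.** The plan's authors "expect that 30% of the LMA group will meet failure criteria" and conclude that "a sample of 130 patients (65 per group) will be needed to conclude non-inferiority", using a 20% margin, one-sided alpha 0.05 and beta 0.20. No design effect appears.
- **Data files.** Under Confidentiality, the analysis dataset is limited to code numbers and study data. Names, record numbers and birth dates sit in a separate file for cross-checking. No family identifier is described, though the data collection sheet is not in the text available for review.

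**The concern.** Siblings share gestational age, antenatal steroid exposure and usually the circumstances of delivery, so their respiratory outcomes are plausibly correlated. They also fall in the same gestational-age stratum. If they are enrolled together, the next-envelope procedure would give them adjacent places on a blocked list, which tends to put them in opposite arms.

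A test that assumes independence then has the wrong standard error, and the direction depends on allocation. With siblings split between arms, the positive correlation reduces the true variance of the difference, so the usual standard error is too large and a little power is lost. With siblings in the same arm, the usual standard error is too small, and non-inferiority would be declared too often at the margin. Because the plan states no sibling rule, the direction cannot be read from it.

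**Working it through.** **1. The plan's own figure.** Inputs from the Sample size paragraph: LMA failure 30%, margin 20% (read as absolute percentage points), one-sided alpha 0.05, power 0.80. The INSURE rate is not stated; 30% is assumed.

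n per arm = (1.645 + 0.842)² × (0.3×0.7 + 0.3×0.7) / 0.20² = 64.92, rounded up to 65, so 130 in total. The figure reproduces, and it assumes independent infants.

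**2. Effect of sibling pairs on the variance.** Let S be the number of same-arm pairs, D the number of split pairs, ρ the within-pair correlation of failure and N = 130. Each same-arm pair adds a covariance term and each split pair subtracts one:

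ratio of true to naive variance = 1 + 2ρ(S − D)/N.

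With a share f of infants in pairs (S + D = fN/2) and a fraction d of pairs split, this becomes 1 + fρ(1 − 2d).

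**3. How often adjacent envelopes split a pair.** With blocks of size b, two adjacent places lie in the same block with probability (b − 1)/b and are then split with probability b/[2(b − 1)]. Otherwise they straddle two blocks and are split half the time. So d = 1/2 + 1/(2b):

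- blocks of 2: d = 0.75
- blocks of 4: d = 0.625
- larger blocks: d tends to 0.5 and the effect disappears.

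**4. Results.** f, ρ and b are assumptions. The true one-sided error is 1 − Φ(1.645/√ratio).

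| Allocation | f | ρ | d | Ratio | Error |
|---|---|---|---|---|---|
| Adjacent envelopes, blocks of 4 | 0.20 | 0.3 | 0.625 | 1 − 0.06×0.25 = 0.985 | 4.9% |
| Adjacent envelopes, blocks of 4 | 0.30 | 0.5 | 0.625 | 1 − 0.15×0.25 = 0.963 | 4.7% |
| Adjacent envelopes, blocks of 2 | 0.40 | 0.5 | 0.75 | 1 − 0.20×0.50 = 0.90 | 4.1% |
| Siblings allocated independently | any | any | 0.5 | 1.00 | 5.0% |
| Siblings in the same arm | 0.30 | 0.5 | 0 | 1 + 0.15 = 1.15 | 6.3% |

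**5. Power.** With 65 per arm the naive standard error is √(0.42/65) = 0.0804, and power with no siblings is Φ(0.20/0.0804 − 1.645) = 80.0%. At the ratio of 0.90, the unadjusted test has power Φ[(0.20/0.0804 − 1.645)/√0.90] = Φ(0.889) = 81.3%. A test using the correct variance has 83.6%. Ignoring the pairing therefore forgoes about 2 points of power at most in this range, and does not take power below the planned 80%.

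**6. Simulation check.** 15,000 trials per setting, three strata, one-sided unpooled Wald test at the 20-point margin, sibling outcomes correlated through a latent normal variable.

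| Setting | Error | Power |
|---|---|---|
| No twins, blocks of 4 | 4.5% | 80.7% |
| 30% in pairs, latent correlation 0.5, blocks of 4, split by envelope | 4.5% | 81.0% |
| 30% in pairs, latent correlation 0.8, blocks of 2, split by envelope | 4.2% | 81.3% |
| 30% in pairs, latent correlation 0.8, same arm | 6.5% | 78.6% |

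The fair baseline here is the 4.5% seen with no twins, not 5%: this test falls below its nominal level before any sibling enters.

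**The case against.** The strongest reply is that siblings taking consecutive envelopes is an inference. The text on opening envelopes says nothing about siblings. Each infant must meet the oxygen requirement, the age limit and the other criteria in its own right, so co-twins may qualify at different times, or only one may qualify. A baseline row for multiple gestation also counts a twin enrolled alone, so it does not show that pairs will be enrolled. All of this stands, and it is why the effect can be given only as a range.

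A reader might infer that the planned standard errors are materially wrong, or that false claims of non-inferiority are inflated. The documents do not support that. Under individual randomization, the natural reading, the unadjusted test is correct on average or slightly conservative. Inflation needs siblings kept in one arm, which no section describes. Nor should the whole gap between a simulated error rate and 5% be put down to siblings, since the no-twin rate is already about 4.5%.

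The plan also names only chi-square for the primary outcome, so the error rates above describe a non-inferiority test supplied for this check. Family links might be recoverable from the identified file, and the unseen data sheet may already hold one. These points limit the size and certainty of the finding. They do not remove the omission: no sibling rule is stated, and no named method allows for family correlation.

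**Conclusion.** The point holds as a minor omission. Siblings can be enrolled and appear to be randomized as individuals, yet the analysis treats all infants as unrelated. Under the assumptions above, the true variance is about 0.90–0.985 of the naive one with adjacent envelopes (error about 4.1–4.9% instead of 5%). It equals the naive variance on average with independent allocation, and is about 1.15 times it (error about 6.3%) only with siblings in one arm.

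N = 130 need not change under individual randomization. Only if the stated rule turned out to keep siblings together would the size need another look: 64.92 × 1.15 = 74.7, or 75 per arm, at 30% in pairs and correlation 0.5.

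The share in pairs, the correlation and the block size are assumptions. Triplets were not modelled. The secondary outcomes were not quantified; the same reasoning applies to them with their own correlations.

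**What to change.** 1. State how siblings are allocated: separately, together, or one infant per family.
2. Carry a mother or family identifier in the coded dataset, so that siblings can be linked without reopening the identified file.
3. Compute the primary risk difference and its non-inferiority bound with a variance clustered on mother, for example GEE with identity link and independence working correlation. The point estimate stays the simple difference in proportions, and the variance is valid whether siblings are split or share an arm. With 20–40% of 130 infants in pairs there would be 117 to 104 families (13 pairs plus 104 single infants, to 26 pairs plus 78), enough for a robust variance.
4. Use the same approach for the main secondary outcomes.

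The cost is one data field, a line or two of text and slightly more analysis work. No additional infants are needed if siblings are randomized individually.
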